### 9.7.4. The Statistical Analysis for the SCRI

In the SCRI methodology, each ABRYSVO-vaccinated beneficiary serves as their own control as we assess the risk of experiencing GBS during a pre-defined post-vaccination risk interval to a post-vaccination control interval within the same individual (Section 9.1.2.1). The study population will include all exposed individuals that meeting the inclusion and exclusion criteria, but only individuals who develop GBS cases will contribute to the analysis. This approach inherently controls for time-invariant confounding variables and is a widely recognized method in vaccine safety research but may be susceptible to time-varying

60+y & 0,1 CCI

<sup>11 Pfizer's preliminary analysis in Optum's de-identified Market Clarity Data, previously presented to the FDA in a document titled "Request for Comments and Advice Regarding RSV Vaccine Safety Study (28 August 2024)".

confounding, which can be minimized by choosing a control interval close to the risk interval.

In the analysis, GBS cases that occurred within the first 84 days following vaccination will be included and separated out into the risk and control window. The population summary statistics will be provided for each window.

A conditional Poisson regression model will be used to estimate the IRR and 95% CI, offset by the length of observation time. The model will include an indicator for the risk window as the predictor variable, an offset equal to the log of the window length and will condition on an identification variable for the beneficiary. The model can be written as:

$$log(p) = \beta(risk \ window) + log(interval) + strata(beneficiary \ id)$$

where *p* is the risk of GBS, *interval* represents the length of the respective window in days, and *beneficiary id* is the term identifying the patient. In the primary analysis, the risk window is 1-21 days post-vaccination, and the control window is 43-84 days post-vaccination. In the secondary analysis, the risk window is 1-42 days post-vaccination, and the control window is 43-84 days post-vaccination. Under this model, our null and alternative hypotheses are:

$$H_0$$
:  $e^{\beta} = 1$  (i.e., IRR = 1)

$$H_a$$
:  $e^{\beta} \neq 1$  (i.e.,  $IRR \neq 1$ )

where  $e^{\beta}$  is the IRR of GBS in the risk window compared to the control window. Thus, the significance of the coefficient on the risk window variable at a pre-specified level will indicate a significant association between RSV vaccination and GBS. The statistical significance will be determined using a two-sided hypothesis test of increase using a significance level of 0.05.

The attributable risk (AR) will also be presented for both the primary (21-days risk window) and secondary (42-day risk interval) analyses, and will be defined as:

- X events per 1 million doses
- X events per 100,000 person-years

The AR per million vaccinations (or per 100,000 person-years) will be calculated by subtracting the expected number of events in the risk and control windows using the IRR estimated from the conditional Poisson regression and multiplying this by the total number of adjusted GBS cases to obtain the expected number of cases in each period. The excess number of outcomes will be obtained by finding the differences between the expected number of cases in the risk and control window. The AR per 1,000,000 vaccine doses (or per 100,000 person-years) will then be calculated by dividing the excess number of outcomes associated with vaccination by the number of eligible doses (or eligible person-years) and multiplying by 1,000,000 (or 100,000 for person-years).

<sup>12 When calculating the attributable risk (AR) for the primary risk window of 1-21 days post-vaccination, the number of cases in the control window must be divided by 2 to normalize the length of the risk window to the length of the control window. This will not be done for the secondary risk window of 1-42 days.

The analysis of AR does not presume a causal relationship between the ABRYSVO exposure and the GBS outcome. Rather, the analysis serves as a method to contextualize the additional risk (i.e., incidence) of the GBS outcome more intuitively, to identify the difference in risk in the exposed window compared to the unexposed window. The AR calculations can highlight associations but not definitively establish causal effect.

The final pooled SCRI analysis will be conducted by aggregating individual-level data from two seasons into one analytic file. Currently, only one dose of ABRYSVO is approved and recommended and evidence suggests RSV vaccines appear to provide protection for at least two RSV seasons. Therefore, revaccination is not anticipated during the study period. In the event where a patient had one more than one vaccination records in the pooled SCRI analysis, this will be flagged as an off-label use and numbers will be reported. Only the first exposure to ABRYSVO will be included in the pooled SCRI analysis.

To examine any change in post-vaccination GBS risk over time in Medicare data, a risk time trend analysis will be conducted using data from two seasons and will be further detailed in the SAP.

Additional adjusted analyses will be conducted and are described in Section 9.7.6.

### 9.7.4.1. Subgroup Analyses

Subgroup analyses may be conducted for the pooled SCRI analysis of 2023/2024 and 2024/2025 RSV seasons, pending sufficient sample size. The following is a list of stratification variables under consideration:

- Gender
- Age
- Race
- Concomitant Vaccines on the index date (Broad: yes vs. no; Individual vaccines: Combined, Influenza, Pneumococcal, COVID-19, Shingles, and others)
- Presence of prior infections (yes vs. no)

### 9.7.5. The Descriptive Analysis for Individuals Aged 60-64 years

Given the more limited age range for commercially insured adults 60-64 years, analyses for this age group will be primarily descriptive. Further inferential analysis (e.g., SCRI) may be considered contingent on sample size.

### 9.7.6. Sensitivity Analyses for the SCRI

This section outlines a multi-faceted approach to address potential biases and confounding in SCRI to evaluate the safety of ABRYSVO vaccination. Details of each analysis and any additional sensitivity analyses that may be conducted will be specified in the SAP.

### 9.7.6.1. Seasonality Adjustment

Given that GBS has been seen to be associated with infections such as wild-type influenza, it may exhibit trends that correlate with specific times of the year, which may introduce bias

into the analysis if not properly adjusted for. To evaluate potential time-varying confounding, the study will adjust for the changing risk of GBS over calendar months. Baseline outcome risk will be estimated from a similar population during the same calendar months in the 2022/2023 season and will be included as an offset term in the Poisson regression model.

### 9.7.6.2. Positive Predictive Values (PPV)-Adjusted Quantitative Bias Analysis

A PPV-adjusted analysis will be conducted to assess bias due to outcome misclassification and uncertainty in the claims-identified cases of GBS. Misclassification can occur if cases of GBS are under-identified or if other conditions are mistakenly classified as GBS.

The PPV-adjusted analysis will be performed using quantitative bias analysis (QBA) using PPVs available from prior studies that have conducted medical record review to validated GBS diagnoses following vaccine exposures.(12) The PPV estimate for GBS in CMS Medicare database for individuals aged 65 or older that will be used for adjustment in the study is 71.0% (95% CI: 63.0%, 79.0%).(9) For the SCRI analysis, differential PPV adjustment will also be used based on the FDA's October 2024 ACIP presentation, which reported different PPVs for GBS diagnosis in the risk and control intervals: 62.3% (48.8 - 74.1%) for claims-identified GBS cases during the 1-42 day risk interval and 81.8% (61.5 - 92.7%) during the 43-90 day control interval.(24) The study will integrate updated information on PPVs as they become available in the published literature or regulatory studies for the duration of the study.

# 9.7.6.3. The PPV-adjusted sensitivity analysis will also be conducted in the RCA. Seasonality and PPV-Adjusted Analysis

A seasonality and PPV-adjusted analysis may also be considered, as feasible, to account for both potential confounders that could bias outcome rate estimates.

# 9.7.6.4. SCRI Analysis Stratified by Individuals With and Without the Full Follow-up Period

In the primary analysis, incomplete follow-up for individuals (e.g., due to death, disenrollment, etc.) will be accounted for by using an offset term in the conditional Poisson regression model. To further evaluate potential biases associated with incomplete follow-up, if a significant number of individuals are lost to follow-up in the primary analysis, an SCRI analysis may be conducted requiring complete follow-up period of 84 days.

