vaccination control interval within the same individual. The study population will include all exposed individuals that meet the inclusion and exclusion criteria, but only individuals who develop GBS cases will contribute to the risk estimation. In the analysis, all GBS cases that occur within the specified risk and control intervals following vaccination will be included and the incidence will be estimated separately for the risk and control windows. A conditional Poisson regression model will be used to estimate the IRR and 95% CI, offset by the length of observation time. In addition, sensitivity analyses for addressing potential biases in the SCRI include a seasonality adjusted analysis to account for time-variant confounding, PPV-adjusted quantitative bias analysis for more comprehensive capture of the outcome using published PPV from Medicare data, and an approach adjusted for both seasonality and PPV. A final pooled SCRI analysis will be conducted by aggregating individual-level data from two seasons into one analytical file. Subgroup analyses and a risk trend analysis may also be conducted in the pooled SCRI analysis.

For commercially insured adults 60-64 years, the incidence of GBS after ABRYSVO vaccination will be described. Inferential analysis, SCRI, may be considered contingent on sample size. Other sensitivity analyses may include, but are not limited to, removal of GBS cases that occurred among individuals with prior infection diagnoses for the SCRI and RCA analytic population, a secondary risk interval for the RCA, alternative background rate comparation for the RCA, and a case-centered GBS analysis to evaluate the severity of GBS and relevant risk factors for the SCRI and RCA analytic populations, as well as the descriptive analysis population from PharMetrics Plus.

Detailed methodology for the statistical analyses of data collected in this study will be documented in a statistical analysis plan (SAP).

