## 9.1.2.1. The Study Periods of SCRI Methodology

[figure not shown]
The SCRI analysis spans the 2023/2024 and 2024/2025 RSV seasons, and the follow-up period consists of the pre-specified post-vaccination risk and control intervals. The key study periods of the SCRI analysis are described below:

- Study Periods:
  - o **2023/2024 Study Period:** 31 May 2022 23 May 2024
    - **Indexing period:** 31 May 2023 29 February 2024

- o **2024/2025 Study Period:** 31 May 2023 23 May 2025
  - Indexing period: 31 May 2024 28 February 2025
- o Combined two season study period: 31 May 2022 23 May 2025
  - **Indexing period:** 31 May 2023 28 February 2025
- Note: As detailed in Section 9.1.2, the indexing period will end in February as >90% of RSV vaccinations are anticipated to be administered by that time, as a trade-off to balance timely analyses and more complete data capture.
- Index Date: The date of ABRYSVO administration
- **Baseline period:** 365 days prior to the index date
- Follow-up period:
  - Post-vaccination risk period: 1-21 and 1-42 days after the index date as the primary and secondary risk interval, respectively. Days 22-42 after the primary 1-21 days risk interval will be considered a washout period and will not be included in the analyses to avoid any carryover effects.
  - o **Post-vaccination control period:** 43-84 days after the index date

Figure 3 shows the study design and key study periods of the SCRI analysis.

[figure not shown]
Figure 3. Study design of the self-controlled risk interval analysis

Abbreviations: Dx, diagnosis; GBS, Guillain-Barre syndrome; RSV, Respiratory Syncytial Virus.

Figure 4 shows the study period of SCRI analysis in relation to the RSV seasons.

Figure 4. The study period of self-controlled risk interval analysis during 2023/2024 and 2024/2025 RSV seasons

Abbreviations: GBS, Guillain-Barre Syndrome; RSV, respiratory syncytial virus; SCRI, self-controlled risk interval.

Note: The data maturation period allows for claims in the CMS Medicare FFS administrative database to be completed in the system. Historically, approximately 90% of Medicare IP and OP claims were submitted to the CMS within 2 months after service date. (14, 15)

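### The SCRI offset is defined two ways; if it shortens windows at death, deaths caused by GBS bias the IRR downward, and the 84-day check only partly removes this

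*Protocol*

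**What the plan says.** The protocol describes the SCRI offset in three places.

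- Section 9.7.6.4, on the primary analysis: "incomplete follow-up for individuals (e.g., due to death, disenrollment, etc.) will be accounted for by using an offset term". Death is the first example given. If many people are lost to follow-up, "an SCRI analysis may be conducted requiring complete follow-up period of 84 days".
- Abstract, Data analysis: the conditional Poisson model is "offset by the length of observation time". Section 9.7.4 opens its model description with the same phrase.
- Section 9.7.4, in the next sentence: the model has "an offset equal to the log of the window length and will condition on an identification variable for the beneficiary". The interval term in the equation is then defined as the length of the respective window in days.

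The design features that matter here are also fixed. "In the primary analysis, the risk window is 1-21 days post-vaccination, and the control window is 43-84 days post-vaccination". Section 9.1.2.1 adds that "Days 22-42 after the primary 1-21 days risk interval will be considered a washout period". Section 9.7.4 states that "only individuals who develop GBS cases will contribute to the analysis". Section 9.7.7.3 lists death as an indicator of GBS severity. Nowhere does the protocol separate death caused by GBS from other reasons for incomplete follow-up.

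**The concern.** An offset can account for death only if the person's windows are shortened at death. That is sound when the end of follow-up has nothing to do with the event. It is not sound when GBS itself ends follow-up, because observed time then depends on when the event occurred.

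The bias has one direction because the control window always comes second. An early case who dies loses control time, or all of it. A control-window case has already completed the risk window and can lose only control time.

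At stake is a safety estimate resting on few events, in which some fatal cases soon after vaccination would carry no weight. The error runs toward finding no elevated risk.

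**Working it through.** **1. The protocol's own figure.** The protocol gives no figure for this bias. Its Table 1 anchors the expected case counts. With equal windows (r = 0.5), two-sided alpha 0.05, power 80% and b = ln(IRR):

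n = (1.960 + 0.842·√B)² / A, where A = 2[p·b − ln(r·e^b + 1 − r)], B = b²·p(1 − p)/A, p = IRR/(1 + IRR).

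For IRR 3: A = 2(0.824 − 0.693) = 0.2616; B = 1.207 × 0.1875/0.2616 = 0.865; n = 28.8, so 29 events, as in Table 1. Control events are 29/4, rounded up to 8. The background risk is 4.6 per 100,000 × 21/365.25 = 2.6 per million, and 8/0.0000026 = 3,076,923, also as in Table 1. All seven rows reproduce.

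**2. Expected cases (Section 9.5 inputs).** For 1 million vaccinees, the control window yields 4.6e-5 × 42/365.25 × 1,000,000 = 5.3 cases and the 21-day risk window 2.6 × IRR. That is about 8 cases per season at IRR 1 and 18.5 at IRR 5. For the pooled 2 million at IRR 3, it is about 16 risk-window and 11 control-window cases.

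**3. One case's contribution.** With r and c the risk and control days used in the offset, a risk-window case contributes r·IRR/(r·IRR + c).

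- Death on day 15 after risk-window onset, windows cut: r = 15, c = 0. The contribution is 1 for every IRR, so the case carries no information.
- The same case with planned windows: 21·IRR/(21·IRR + 42), which is informative.
- Death on days 43-84, windows cut: the case stays in with c < 42. This raises the fitted risk-window probability at any given IRR and so lowers the estimate.

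**4. Size of the bias.** Assumptions not in the protocol: a fraction f of cases die of GBS; time from onset to death is exponential with mean m days; onset is uniform within each window. The large-sample IRR solves Σ[I(risk) − r·IRR/(r·IRR + c)] = 0 over cases.

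Two parts have a closed form. The share of primary risk-window cases lost entirely is f·[1 − (m/21)(e^(−21/m) − e^(−42/m))]. For f = 10%, m = 14: 0.10 × [1 − 0.667 × (0.223 − 0.050)] = 8.8%.

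For the complete-84-day restriction, with f = 10% and m = 14, 99.4% of fatal risk-window cases and 68.3% of fatal control-window cases die before day 84. The IRR is multiplied by (1 − 0.0994)/(1 − 0.0683) = 0.967.

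Primary analysis; paired values are for m = 14 / 28 days:

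| f | Risk-window cases lost | True IRR 1, windows cut at death | True IRR 3, windows cut at death | Complete-84-day analysis, % low |
|---|---|---|---|---|
| 3% | 2.7% / 2.0% | 0.96 / 0.97 | 2.90 / 2.92 | 1.0 / 1.4 |
| 5% | 4.4% / 3.3% | 0.94 / 0.95 | 2.84 / 2.87 | 1.6 / 2.3 |
| 10% | 8.8% / 6.7% | 0.88 / 0.90 | 2.67 / 2.73 | 3.3 / 4.7 |
| 15% | 13.3% / 10.0% | 0.82 / 0.86 | 2.51 / 2.60 | 5.2 / 7.2 |

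Planned window lengths return the true IRR in every row. The 1-42 day risk window behaves similarly: at f = 10% and true IRR 1 it gives 0.90 / 0.92.

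**5. Against sampling error.** Pooled, 16 versus 11 cases gives IRR (16/21)/(11/42) = 2.91, exact 95% CI 1.27-6.93. Losing one, two or three risk-window cases gives 2.73 (1.17-6.57), 2.55 (1.07-6.20) and 2.36 (0.98-5.83). The expected loss at f = 10%, m = 14 is 16 × 8.8% = 1.4 cases.

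**The case against.** The strongest reply is that cutting windows at death is inferred. The only written equation, in Section 9.7.4, uses "an offset equal to the log of the window length"; with fixed lengths of 21 and 42 days there is no bias of this kind. Section 9.7.6 leaves detail to the SAP, which may settle it. This stands in part: the protocol conflicts with itself rather than stating the rule outright. But Section 9.7.6.4 speaks of the primary analysis, and its claim that the offset deals with death has no meaning under fixed lengths.

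A reader might infer that every fatal risk-window case disappears. That is too broad: only those who die before day 43 drop out of the estimate, and Section 9.7.7.3 still describes death and time to onset for all identified cases (subject to the suppression of counts below 11 in Section 9.6).

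A reader might also infer that the planned check cannot reveal the problem. The numbers do not support that. At f = 10% and m = 14, the complete-84-day analysis gives 0.97 where the primary gives 0.88 (true IRR 1), and 2.90 where the primary gives 2.67 (true IRR 3). A rise between the two analyses would be a warning. What remains is that the check is optional, leaves a residual in the same direction, and would be hard to read with so few cases.

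Finally, the size is uncertain and modest beside sampling error. Losing the three cases that would move the pooled interval across 1 means losing 3/16 = 19% of risk-window cases, above the highest scenario in the table (13%).

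**Conclusion.** The point holds as a conflict to reconcile with a one-directional consequence. If windows are cut at death, as Section 9.7.6.4 and the abstract most naturally imply, death caused by GBS biases the IRR downward. Deaths unrelated to GBS, and disenrollment, are handled properly by an observed-time offset.

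Under the assumed 3-15% fatality and 14-28 day mean, the IRR is about 2-18% low across both risk windows, and the complete-84-day analysis about 1-7% low. No firm size can be claimed, because the protocol gives neither case fatality nor time to death. The protocol should be corrected before the final SCRI analyses, but the issue is not severe enough to put the design in doubt.

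**What to change.** - In Sections 9.7.4 and 9.7.6.4 and the abstract, give one definition of the offset.
- For cases who die after GBS onset, use the planned lengths: 21 or 42 risk days and 42 control days. Shorten windows only for censoring unrelated to the event (disenrollment, end of data).
- Report the observed-time offset as a sensitivity analysis, so that the effect of the choice is visible.
- Change the complete-follow-up check to require enrolment to day 84 or death.

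The cost is wording and a small change to the offset code. The downside is that planned windows slightly overcount control time for deaths unrelated to GBS. If annual mortality is 4% (an assumption), the gap of 52.5 days between window midpoints gives 0.04 × 52.5/365.25, or about 0.6% upward on the primary IRR.

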### 9.7.7. Additional Sensitivity Analyses

This section outlines further sensitivity analyses in SCRI and/or RCA that may be considered to evaluate the safety of ABRYSVO vaccination. Details of each analysis and any additional sensitivity analyses will be specified in the SAP.

# 9.7.7.1. Removal of GBS Cases After Infection Diagnoses for the SCRI Analytic Population

Prior infection has been found to be one of the most important risk factors for GBS.(31) In this study, we will conduct a sensitivity analysis, excluding individuals that have a prior respiratory or gastrointestinal infection within 1-42 days prior to GBS onset. These

individuals will not be included in the risk estimation for the SCRI analysis as their GBS onset may be related to their prior infection rather than the vaccination.

### 9.7.7.2. Secondary Risk Interval for the RCA Analytic Population

For the RCA, a secondary risk interval of 1-42 days post-index will be used a sensitivity analysis in lieu of the primary risk interval of 1-21 days post-index. The risk window of 42 days post-vaccination is generally recommended by the Brighton Collaboration GBS case definition as the most comprehensive risk interval, although current reports to VAERS suggest >90% of GBS events after RSV vaccinations occurred within 21 days and all are within 22 days. (19) Extending the window to 42 days helps ensure that all potential cases are captured, providing a comprehensive assessment of risk, and is consistent with the intervals defined for the SCRI. (9, 18, 19) Furthermore, a risk interval of 1-21 days will also be analyzed within this population to ensure comparability to the primary analysis.

# 9.7.7.3. Case-Centered GBS Analysis for the SCRI Analytic Population, the RCA Analytic Population and the Descriptive Analysis Population

To enhance the understanding of the severity and characteristics of the GBS cases identified in our analysis, and to better understand the risk factors of the individuals with GBS onset, a case-centered analysis will be performed to inform decisions regarding preventing severe outcomes. For each patient with a case of GBS identified, the following variables will be assessed:

- Selected demographics and clinical characteristics;
- Mean time to onset of GBS following index date;
- GBS risk factors (e.g., age, gender, preceding infections prior to onset, surgery within 42 days before GBS onset);
- Co-vaccination, stratified by risk and control intervals;
- Neurologist encounter surrounding the GBS diagnosis and diagnosing procedures received;
- Indicators of GBS severity: duration of IP stay, death (yes/no), respiratory failure or intubation. These variables will be assessed as part of the inpatient stay with a primary discharge diagnosis of GBS, following the definitions in the study of Shingles vaccination and GBS by Goud et al, 2021. (23)

